3. Currently maintained on antiviral therapy for at least 48 weeks with any HBV DNA value at Screening/Baseline and planned to be switched to TAF by their physician

4. Routinely monitored for serum HBV DNA PCR, liver chemistry, renal chemistry including by their physicians every 3-6 months and a bone density scan at least every 2 years as per routine clinical care (one at baseline and one 2 years after switch).
5. Estimated creatinine clearance $> 15 \text{ ml/min}$ for men or $> 12.75 \text{ ml/min}$ for women (using the Cockcroft-Gault method) at Screening/Baseline Visit
6. Willing and able to provide informed consent
7. Able to comply with dosing instructions for study drug administration and able to complete the study schedule of assessments

Exclusion criteria:

1. Pregnant women, women who are breastfeeding or who believe they may wish to become pregnant during the course of the study
2. Previous recipient of a liver transplant
3. Co-infection with human immunodeficiency virus (HIV) or hepatitis C (HCV) or hepatitis D (HDV)
4. Severe or uncontrolled comorbidities
5. Current or known hepatic decompensation (≤ 2 years) (e.g ascites, encephalopathy, or variceal hemorrhage) with a Child-Pugh score of B or C
6. Malignancy including liver cancer within 5 years except cancers easily curable by surgical resection (e.g. basal cell skin cancer and squamous cell cancer)
7. Currently receiving any immunosuppressive therapy
8. On any of the disallowed concomitant medications listed in the prior and concomitant medications list (pg. 13). Subjects on prohibited medications who are otherwise eligible will need a wash out period of at least 30 days prior to the Screening/Baseline visit.
9. Males and females of reproductive potential who are unwilling to use “effective” protocol-specified method(s) of contraception during the study.
10. Current substance or alcohol abuse judged by the investigator to potentially interfere with subject compliance.
11. Any other clinical conditions that, in the opinion of the Investigator, would make the subject unsuitable or unable to comply with any of the study procedures

4. Study Objectives

Primary objective:

- To describe rate of persistence and/or improvement of viral suppression with TAF as with previous anti-HBV treatment

Secondary objective:

- To describe persistence of ALT normalization and/or improvement of ALT levels with TAF as with previous anti-HBV treatment

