- To describe trends in serum creatinine and calculated creatinine clearance as available by local labs.
- To describe trends in bone mass from baseline to 24 months after switch.

5. Study Design

Study design: Open label prospective interventional cohort study.

Study Timelines:

[figure not shown]
- Total study duration: 36 months
- Study Start-Up: 3 months
- Patient enrollment: 6 months
- Patient follow-up: 24 months
- Final analysis & Manuscript Preparation: 3 months
- Publication plan: Interim analysis 2018 – 2019, Final analysis 2020

Primary endpoint: Rate of viral suppression at 6, 12, 18, 24 months after switch, as available.

Secondary endpoints(s):

- ALT levels at 6, 12, 18, 24 months after switch
- Serum creatinine, calculated creatinine clearance (Cockcroft-Gault) at 6, 12, 18, 24 months after switch
- % change in bone mineral density from baseline to 24 months after switch

Study schematic:

Study protocol: Treatment Outcomes in Chronic Hepatitis B Patients on Sequential Therapy with Tenofovir Alafenamide

The following table below describes all study procedures:

Study protocol: Treatment Outcomes in Chronic Hepatitis B Patients on Sequential Therapy with Tenofovir Alafenamide

Study Procedures	Screening/Baseline	Treatment Months*							
		3*	6	9*	12	15*	18	21*	24/ED
Informed Consent	X								
Inclusion/ Exclusion Criteria	X								
Medical History ¹	X								
Vital Signs	X		X		X		X		X
Physical Examination	X		X		X		X		X
Adverse Events			X		X		X		X
Concomitant Medications	X		X		X		X		X
Bone Density Scan (DEXA) ^{4,5}	X								X
HBeAg ²	X		X		X		X		X
HBV DNA PCR	X	X	X	X	X	X	X	X	X
α -fetoprotein (AFP)	X		X		X		X		X
Ultrasound (to rule out HCC)	X		X		X		X		X
International Normalized Ratio (INR) ³	X				X				X
CBC Panel with WBC, Hb, Platelet, HCT	X		X		X		X		X
Complete Metabolic Panel with Na, K, Cr, Tb, CO2/HCO3, BUN, GLU, AST, ALT, ALK, ALBU	X	X	X	X	X	X	X	X	X
Serum Phosphorus	X	X	X	X	X	X	X	X	X
Fasting Cholesterol Panel with Total Cholesterol, HDL, direct LDL, TG	X		X		X		X		X
Vitamin D Assessment	X								
Fibrotest, Fibrosure, Fibrospect, FIB-4 or Elastography	X								
HCV, HDV, HIV Testing ⁶	X								
Urinalysis	X	X	X	X	X	X	X	X	X

Study protocol: Treatment Outcomes in Chronic Hepatitis B Patients on Sequential Therapy with Tenofovir Alafenamide

Data capture/case report forms	X		X		X		X		X
Study Drug Dispensing	X		X		X		X		X

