*Every visit can be 3-6 months as per routine clinical care. Clinical visit for Month 3 is optional but Month 3 lab is required for all sites. Month 9, 15, and 21 labs are optional.

1. For women of childbearing potential, last menstrual period must be documented
2. HBeAg serology to be done only in patients with positive HBeAg at Screening
3. INR testing to be done only in cirrhotic patients
4. Bone density scan will be charged and billed to the study as applicable.
5. Additional scan at 12 months is optional per investigator.
6. HCV RNA or antibody testing can be used to rule out co-infection. HDV and HIV antibody test are optional if test is not available to order at site or is not routinely performed.

Study Procedures:

Pre-Screening: Patients who are planned to be switched from their current antiviral therapy to TAF will be identified by their primary physician and approached to enroll in this prospective interventional cohort study. If a patient is deemed eligible to participate, the site will evaluate the potential patient using the inclusion/exclusion criteria and fill out the CRF for the screening visit. The local coordinator will transmit the pre-screening data to the central coordinator prior to the actual screening/baseline visit. If the patient is deemed eligible by the sponsor, the patient will be given a study ID and allowed to enter the study.

Screening/Baseline: Written and informed consent will be obtained prior to any study protocol related procedures or data abstraction. If patient has been pre-screened approved and all lab data are available they will begin treatment with TAF on the screening/baseline visit. The screening/baseline visit consists of obtaining written and informed consent, reviewing the inclusion/exclusion criteria, confirming medical history, completing a physical examination with vital signs and body weight, reviewing any concomitant medications and study drug dispensing. HBV DNA can be done within 3 months prior to study enrollment and Vitamin D assessment can be done within 12 prior to study enrollment. Serum AFP and liver ultrasound can be done within 6 months prior to enrollment. DEXA scan can also be done within 6 months prior to enrollment.

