Procedures: In general, labs should include CBC (complete blood count, e.g. WBC, PLT, Hb, HCT), CMP (complete metabolic panel, e.g. CO₂ or HCO₃⁻, Na⁺, K⁺, Creatinine, Albumin, ALT, AST, ALK, Glucose, Total Bilirubin, BUN, Serum Phosphorous), INR (international normalized ratio), AFP (alpha-fetoprotein), fasting cholesterol panel, (e.g. Total cholesterol, HDL, direct LDL, Triglycerides (TG), Urinalysis, HBV DNA quantification and HBeAg status. Screening will also include HCV, HIV and HDV testing, if not previously done. All laboratory tests including the DEXA scan for all sites except South Korea will be ordered and billed as per routine care. For South Korea, all laboratory and DEXA scans will be ordered and billed to the study per standard of procedures in South Korea for all studies that provide medication. For Taiwan and the US, all DEXA scans will be ordered and billed to the study. Blood will be drawn at the site at which the patient was recruited, and processed by a lab technician in the clinical laboratory at that respective site. Standard of care for HCC surveillance should include radiology and AFP every 6 months per AASLD and APASL guidelines. All scans should be billed to patient's insurance or patient. At site PI's discretion, higher level imaging or frequency can be done.

Treatment Visits: Treatment will consist of taking TAF 25 mg daily with food for 24 months. Treatment visits will occur at approximately every 3-6 months as per routine clinical care, except for those listed in section 13. Clinical visit for Month 3 is optional but Month 3 lab is required for all sites. Month 9, 15, and 21 labs are optional. Each visit will consist of reviewing adverse

events and concomitant medications, completing a physical examination with vital signs and body weight, completing all necessary routine labs including DEXA scan and study drug dispensing. At every visit the patient must bring all study drugs (including empty bottles) so that the study staff can count compliance using the number of remaining pills.

This schedule of clinic visits and laboratory tests are routine and standard practice for investigators in their treatment of similar patients with CHB. Patients will be encouraged to adhere to these recommendations. Results of these laboratory tests and clinical evaluations will be recorded as well as any additional evaluations that are done as part of the patient's clinical care that are pertinent to the objective of the study.

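### The primary endpoint is a pooled suppression rate at four separate visits, so it cannot give the persistence or the improvement that the primary objective asks for

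*Combined protocol and SAP*

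**What the plan says.** Section 4 gives the primary objective as "To describe rate of persistence and/or improvement of viral suppression with TAF as with previous anti-HBV treatment". Section 5 gives one primary endpoint: "Rate of viral suppression at 6, 12, 18, 24 months after switch, as available".

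Inclusion criterion 3 (Section 3) admits treated patients "with any HBV DNA value at Screening/Baseline", so the cohort can mix patients who are suppressed at the switch with patients who are not.

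The procedures table in Section 5 marks HBV DNA PCR at baseline and every three months to Month 24. Its footnote, repeated under Treatment Visits, sets the status of the intermediate labs: "Month 3 lab is required for all sites. Month 9, 15, and 21 labs are optional". The table row "Data capture/case report forms" is marked at baseline and Months 6, 12, 18 and 24, but not at Month 3. The text under Treatment Visits nevertheless says "Results of these laboratory tests and clinical evaluations will be recorded".

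Section 8 plans descriptive and comparative statistics with a 95% confidence interval. Neither the objectives, the endpoint nor Section 8 states an HBV DNA cut-off for suppression, defines persistence, links a patient's results across visits, or restricts a denominator by baseline status.

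**The concern.** Persistence is a property of one patient followed over time, and improvement is a property of patients who start unsuppressed. A pooled visit rate measures neither: it is the share of whoever has a result that is suppressed on that occasion. The same series of four rates can arise from a few patients who stay unsuppressed throughout or from many who each lose suppression once.

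The required Month 3 result is the first scheduled on-treatment measurement after the switch, yet no endpoint uses it. The question is whether patients who change to TAF remain suppressed. If the plan is followed as written, the report will not contain that figure. Any persistence figure added later would rest on a definition chosen after the data were seen.

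**Working it through.** **Inputs.** Cohort goals of 185, 33 and 33 and a total of 251 (Section 3); endpoint visits at Months 6, 12, 18 and 24; Month 3 HBV DNA required. The plan's own total reproduces: 185 + 33 + 33 = 251. The documents give no expected suppression rate, so every rate below is assumed.

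**1. Which losses the endpoint can see.** Take a patient suppressed at baseline.
- Unsuppressed at Month 3 only: counted as suppressed at all four endpoint visits, so the loss appears nowhere. The same holds for a loss seen only at Month 9, 15 or 21.
- Unsuppressed at Month 12 only: lowers the Month 12 rate but counts as suppressed at Months 6, 18 and 24. The loss is visible but not tied to a patient.

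**2. What visit rates imply among baseline-suppressed patients with complete data.** If a proportion p is suppressed at each of k visits, the share suppressed at all k lies between max(0, 1 − k(1 − p)) and p. The lower limit needs every loss to fall in a different patient; the upper limit needs the same patients each time. The independent case is p^k.

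| p at each visit | Four visits: range | Four visits: independent | With Month 3 at the same p: range | With Month 3: independent |
|---|---|---|---|---|
| 95% | 1 − 4(0.05) = 80% to 95% | 0.95^4 = 81.5% | 1 − 5(0.05) = 75% to 95% | 0.95^5 = 77.4% |
| 98% | 1 − 4(0.02) = 92% to 98% | 0.98^4 = 92.2% | 1 − 5(0.02) = 90% to 98% | 0.98^5 = 90.4% |

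Results in one patient are likely to be correlated. In a first-order Markov model with correlation ρ between adjacent visits, the four-visit share is p(p + ρ(1 − p))^3. At p = 95% this is 0.95 × 0.975^3 = 88.1% for ρ = 0.5, and 0.95 × 0.995^3 = 93.6% for ρ = 0.9.

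In patients, if all 185 in the entecavir group were suppressed at baseline, a 95% rate means 185 × 0.05 = 9.25 unsuppressed per visit. Over four visits that is at most 4 × 9.25 = 37 different patients. If the same patients are unsuppressed each time, it is about 9.

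**3. What a mixed baseline does.** At one visit the pooled rate is b × keep + (1 − b) × gain, where b is the share suppressed at baseline, keep is the share of those still suppressed, and gain is the share of the others who have become suppressed.
- With b = 0.80, keep = 0.98 and gain = 0.50, the pooled rate is 0.784 + 0.10 = 88.4%. It understates persistence of 98%.
- If 165 of 185 are suppressed at baseline, 10 lose suppression and 10 gain it, the rate is 165/185 = 89.2% before and (155 + 10)/185 = 89.2% after. The unchanged rate conceals that 10 of 165 lost suppression (persistence 155/165 = 93.9%).
- With all patients suppressed at baseline and losses spread over different patients, step 2 shows a 95% visit rate alongside 80% persistence. Here it overstates.

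**The case against.** The strongest reply is that this is a descriptive, uncontrolled pilot study sized by feasibility. Its objective covers improvement as well as persistence, and serial suppression rates are a reasonable cohort-level description of both. No power, error rate or decision rule depends on the form of the endpoint. HBV DNA is drawn at Month 3 and results are to be recorded, so a within-patient summary may still be possible. The wide ranges above come from an assumed rate and the mathematical extreme; at 98% the gap over four visits is at most 6 points.

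Much of this stands. It limits the size of the problem and rules out several stronger readings:
- A reader might infer that the visit rates are an upper bound on persistence. That holds only among baseline-suppressed patients with complete data. The endpoint is not restricted to them, and in the 88.4% example it errs the other way.
- A reader might infer that up to 37 losses would be hidden. Losses at Months 6, 12, 18 and 24 do lower the rate for that visit. What is missing is whether they are the same patients.
- A reader might infer that the plan will classify a patient who loses and regains suppression as persistent. The documents contain no such category; they simply do not prevent that interpretation.

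The reply does not remove the mismatch. Visit rates could describe improvement only if split by baseline status, and no split is planned. The value of a descriptive study lies in describing what its objective names.

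**Conclusion.** The concern holds in this form: as written, the primary endpoint yields neither a persistence rate nor an improvement rate, and it leaves out the required Month 3 HBV DNA. The direction of error is not fixed.

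The size is illustrative. Among baseline-suppressed patients with complete data, a 95% rate at each of the four visits leaves continuous suppression anywhere from 80% to 95%, a gap of up to 15 points; a 98% rate leaves 92% to 98%. With strong within-patient correlation the gap shrinks to 1 or 2 points (95% against 93.6% at ρ = 0.9). The Month 3 extension further assumes the same rate at Month 3.

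The documents do not support saying that the planned rates are biased upward, or that Month 3 results will be unavailable. The change should be made before the final analysis; it does not call the design or the sample size into question.

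**What to change.** - State one HBV DNA cut-off for suppression and use it for every rate.
- Keep the rates at Months 6, 12, 18 and 24, but report them by baseline suppression status.
- Among patients suppressed at baseline, add within-patient persistence over the labs common to all sites: Months 3, 6, 12, 18 and 24. Show any non-suppressed result and two consecutive non-suppressed results separately, so that isolated blips are distinguished from sustained loss. A first non-suppressed result at Month 24 cannot be confirmed and should be listed as such.
- State how a missing visit is handled, for example by time to first loss with censoring at the last HBV DNA, plus a sensitivity analysis. This needs withdrawn patients to contribute up to their last result, whereas Section 8 now limits analyses to patients who have not been withdrawn.
- Among patients not suppressed at baseline, report improvement separately.
- Use the optional Month 9, 15 and 21 labs only in a sensitivity analysis; otherwise sites that test more often would appear to have more losses.
- Confirm that Month 3 HBV DNA is entered in the database, since the case report form row has no Month 3 mark.

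The cost is some added analysis and a clarification of data capture. All the HBV DNA tests are already scheduled, and no visit, patient or sample-size figure changes. Among baseline-suppressed patients with complete data, the share suppressed at every common lab cannot exceed their visit rates, so the sponsor should expect an equal or lower headline figure in that group.

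### The bone density endpoint names no skeletal region and no same-scanner or cross-calibration rule, while any DEXA from the 6 months before enrollment can serve as baseline

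*Combined protocol and SAP*

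**What the plan says.** **Objective and endpoint.** Section 4 sets the secondary objective: "To describe trends in bone mass from baseline to 24 months after switch". Section 5 turns this into a percent "change in bone mineral density from baseline to 24 months after switch". Neither names spine, hip or any other region.

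**Timing.** The Section 5 schedule requires DEXA at Screening/Baseline and at Month 24 or early discontinuation. A 12-month scan is optional. For baseline, the Screening/Baseline paragraph adds: "DEXA scan can also be done within 6 months prior to enrollment". The same paragraph states: "Written and informed consent will be obtained prior to any study protocol related procedures or data abstraction".

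**Ordering.** The statements do not agree.
- Section 3, inclusion criterion 4, describes both the baseline and the 2-year scan as routine care.
- Section 5, Procedures, gives a general rule: "All laboratory tests including the DEXA scan for all sites except South Korea will be ordered and billed as per routine care".
- The same paragraph continues: "For South Korea, all laboratory and DEXA scans will be ordered and billed to the study". It then adds: "For Taiwan and the US, all DEXA scans will be ordered and billed to the study".
- Footnote 4 to the schedule says that scans are charged to the study where applicable.
- Section 13 provides reimbursement for DEXA in the US, Taiwan and Korea. It concedes that these scans may not be routine for all US and Taiwan participants.

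**Location.** Procedures ties blood sampling to the recruiting site. It has no such statement for DEXA.

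**The concern.** A percent change in bone density is interpretable only if both measurements are of the same bone on comparable equipment. Here the baseline value may come from a scan made before the patient consented. Such a scan cannot have been a study procedure, and its only stated condition is its date.

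The background text ahead of Section 3 gives potentially lower bone loss as part of the interest in TAF, and this is the only bone endpoint. Each patient has two mandatory scans. Every cohort switches to TAF, so no concurrent group stays on prior therapy against which a scanner offset could be judged. The document does not say that device and region will be recorded. If they are not, the analyst cannot tell a mismatched pair from a real change. Section 8 sets spurious data to missing, but that helps only if such data can be recognised.

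**Working it through.** **1. What the text permits.** The document gives no precision or power figure for bone density, so there is nothing to reproduce. The check is a reading of every DEXA statement.

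| Requirement | Found in the document? |
|---|---|
| Skeletal region | No |
| Same scanner or facility at both scans | No |
| Cross-calibration or central reading | No |
| Recording of device and region | Not stated (the CRF is not included) |
| Age limit on the baseline scan | Yes, 6 months before enrollment |

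A pair from two scanners, or a spine value set against a hip value, therefore complies with the plan.

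The window also affects the interval. If TAF starts at enrollment, a scan made 6 months earlier gives 24 + 6 = 30 months, of which 6/30 = 20% is on the prior regimen. This is a reason to record the scan date.

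**2. Inputs for size.** From Section 3: cohorts of 185, 33 and 33, which sum to the stated 251. From Section 8: 95% confidence intervals. Assumed, because the document gives no values:
- SD of the 24-month percent change: 3–5 points
- share of pairs with a scanner change: 10–50%
- systematic offset between scanners: 1–3%

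**3. Precision.** Half-width = 1.96 × SD / √n.

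| n | SD 3 | SD 4 | SD 5 |
|---|---|---|---|
| 185 | 0.43 | 0.58 | 0.72 |
| 33 | 1.02 | 1.36 | 1.71 |

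**4. Shift in the mean if all offsets have the same direction.** Shift = share × offset.
- 0.10 × 1% = 0.1 points
- 0.25 × 2% = 0.5 points
- 0.50 × 3% = 1.5 points

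**5. When the middle case matters.** A shift of 0.5 exceeds the half-width at n = 185 only if SD < 0.5 × √185 / 1.96 = 3.47. At SD 3 it needs n > (1.96 × 3 / 0.5)² = 138.3, so at least 139 complete pairs. At n = 33 it is about half of the 1.02 half-width.

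**6. Offsets in mixed directions.** If changed pairs split evenly up and down, the mean does not shift and the added variance is share × offset². At SD 3:
- 25% of pairs with a 2% offset: SD = √(9 + 0.25 × 4) = 3.16. The half-width at n = 185 goes from 0.43 to 1.96 × 3.16 / √185 = 0.46.
- 50% of pairs with a 3% offset: SD = √(9 + 0.50 × 9) = 3.67. The half-width goes to 0.53 at n = 185 and from 1.02 to 1.25 at n = 33.

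**7. Mixed regions.** No offset model is needed here. A percent change from one bone to another does not estimate the endpoint.

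**The case against.** **Nothing says that machines will differ.** This is correct. Patients are identified by the physician who already monitors them, and many pairs may come from one department. The plan leaves a risk uncontrolled; it does not create a known error.

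**A routine baseline against a study-ordered Month 24.** A reader might infer that the two scans follow different ordering routes, so that any offset would differ by country. The documents do not support this. The Taiwan and US sentence covers all DEXA scans, South Korea is also study-ordered, and Japan stays under the general routine-care rule for both scans. The split can arise in those three countries when a pre-consent scan is used, but no rule sets it. The ordering text concerns who requests and pays, not which machine is used. What stands is that the ordering statements contradict one another.

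**The prior-TDF cohort is a comparison.** Section 3 does call it that, and an offset common to the cohorts would cancel in that contrast. It cancels only if scanner changes are equally frequent and alike across cohorts, which nothing ensures. It does not help the change from baseline within a cohort, which is the stated endpoint.

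**Source documents could allow later repair.** Section 9 has sites send de-identified source documents to the central coordinators. This helps if scan reports are among them and state device and region. The plan does not secure that.

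**It is a secondary, descriptive endpoint in a self-described pilot.** This is true, and it limits the weight of the point.

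**Conclusion.** The point holds as an avoidable weakness in the study's only bone endpoint. The plan accepts a baseline scan on its date alone, names no region, and has no same-scanner or cross-calibration rule.

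Its size cannot be fixed from the documents. Under same-direction offsets of 1–3% in 10–50% of pairs, the shift runs from 0.1 points, which is negligible, to 1.5 points, which is larger than the half-width in the entecavir cohort at any SD from 3 to 5. A reader might take the middle case of 0.5 points as proof that bias already exceeds sampling error. It does so only in the cohort of 185, with offsets in one direction, an SD below about 3.5%, and at least 139 complete pairs at an SD of 3%. With mixed directions the result is mainly a wider interval. The finding for mixed regions does not rest on any of these assumptions.

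This should be corrected because prevention is cheap and later repair is uncertain. It does not threaten the primary endpoint or change the sample size.

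**What to change.** - **Baseline scan.** Accept a pre-enrollment DEXA only if it was made at the facility and on the scanner planned for Month 24, or on one with documented cross-calibration, and covers the same regions. Otherwise do the baseline scan already in the schedule.
- **Data capture.** Record scan date, device and region on the CRF at both time points.
- **Endpoint.** Analyse lumbar spine and total hip separately, and compute every change within one region.
- **Analysis.** Show results with and without pairs in which the scanner changed without cross-calibration. This also covers a site that replaces its scanner during the two years.
- **Ordering.** Reconcile inclusion criterion 4, schedule footnote 4 and the Procedures paragraph, and check Section 13 against the result.

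**Cost.** A few CRF fields and a short paragraph. Some outside scans will not qualify, so some patients will need the scheduled baseline scan; who pays depends on the ordering statements being settled. Setting pairs aside widens the interval, mostly in the cohorts of 33. If 25% were set aside, about 25 pairs would remain (33 × 0.75 = 24.75), and at SD 3 the half-width would go from 1.02 to 1.96 × 3 / √25 = 1.18 points. Cross-calibration keeps that loss small.

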- Failure to follow study instructions or protocol violation (subject to investigator)
- Adverse events (subject to investigator)
- Any medical, psychosocial or administrative or other reasons that would, in judgment of the investigator, be detrimental to the patient's well-being.
- Death
- Withdrawal of informed consent – They may be considered withdrawn if they state an intention to withdraw or fail to return for study visits, or become lost to follow-up for any other reasons.

Procedures for Subject Withdrawal:

When and how to withdraw subjects from trial: Subjects will be withdrawn during the study at any time if they meet any of the withdrawal criteria above. If premature withdrawal occurs for any reason a report will be generated by investigator describing reasons and nature of the withdrawal and will include documentation of last patient encounter and laboratory testing prior to or at time of withdrawal. If patient stops the study treatment early, documentation outlining the reasoning will be drawn.

Data to be collected for withdrawn subjects: For patients not lost to follow-up, viral suppression and pertinent clinical and laboratory data to be collected will be those which are done as part of standard clinical care including bone and renal function tests.

Follow-up for subjects withdrawn from investigational product: If patients are withdrawn from the study early, they will complete an Early Discontinuation (ED) Visit, during which they will have a physical exam, review their concomitant medication and any adverse events, review their drug accountability, and complete any routine laboratory, bone density or imaging tests. All patients that have withdrawn from the study early will also complete a follow-up visit 3 to 6 months after their ED visit.

7. Adverse Events and Toxicity Management

Assessment of safety: Safety assessments will include monitoring of laboratory results, vital signs, treatment emergent adverse events, serious adverse events, etc. Safety assessments will be performed at every clinic visit as part of clinical care and during follow-up visits.

Adverse events definitions:

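### Missed visits and loss to follow-up are classed as withdrawal of consent, and everyone withdrawn is left out of the analysis, so non-attenders can drop out of the suppression rate even when their routine HBV DNA is available

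*Combined protocol and SAP*

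**What the plan says.** Section 6, Withdrawal Criteria, has one bullet headed as withdrawal of informed consent that holds three different events. The first two are these: "They may be considered withdrawn if they state an intention to withdraw or fail to return for study visits". The third, loss to follow-up, closes the same sentence. The bullet sets no number of missed visits, no time window and no contact attempts.

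The bullet is permissive, but the paragraph on when and how to withdraw subjects is not: "Subjects will be withdrawn during the study at any time if they meet any of the withdrawal criteria above".

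Three rules then apply after withdrawal, all in Section 6:

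- Data: "For patients not lost to follow-up, viral suppression and pertinent clinical and laboratory data to be collected" come from standard care. Only patients lost to follow-up are left out.
- Early discontinuation visit: "If patients are withdrawn from the study early, they will complete an Early Discontinuation (ED) Visit".
- Later visit: "All patients that have withdrawn from the study early will also complete a follow-up visit 3 to 6 months after their ED visit".

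Section 8, on the selection of subjects for analysis, admits only eligible subjects who have not been withdrawn. Section 8 also treats missing data as an empty field and gives no further method. The primary endpoint in Section 5 is the rate of viral suppression at 6, 12, 18 and 24 months after the switch, as available.

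**The concern.** Not attending a study visit is a different event from refusing to take part, and in this trial the difference affects the results. Inclusion criterion 4 requires patients already monitored by their own physicians, with HBV DNA measured every 3 to 6 months. The footnote to the schedule of procedures adds "Every visit can be 3-6 months as per routine clinical care". A patient can thus miss a study visit and still have a usable HBV DNA result in the clinic record.

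Once that patient is labelled withdrawn, Section 8 removes the patient from the analyses. Read literally, it removes the whole subject, including time points reached before withdrawal. Patients who stop attending may plausibly be less adherent and so less often suppressed. If so, a rate computed only in those never withdrawn overstates suppression after the switch. The plan has nothing that would offset this: there is no missing-data method, and Section 5 marks measures against bias as not applicable.

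A second problem is independent of the first. The two post-withdrawal visits and the data rule apply to withdrawn patients without saying what happens when the reason was revoked consent. A site has no instruction for that case.

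**Working it through.** **1. The rules side by side, by type of patient**

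| Patient | Withdrawn under Section 6? | Standard-care data still collected? | Both later visits required? | Analysed under Section 8? |
|---|---|---|---|---|
| States a wish to withdraw | Yes | Yes, no exception visible | Yes, no exception visible | No |
| Misses study visits, still in routine care | May be (bullet); will be (next paragraph) | Yes, because not lost to follow-up | Yes, if withdrawn | No, if withdrawn |
| Lost to follow-up | May be (bullet); will be (next paragraph) | No, expressly left out | Yes as written, if withdrawn | No, if withdrawn |

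The second row carries the point: the result is collected under Section 6 and then excluded under Section 8. The first row carries the separate consent point.

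**2. The plan's own figure**

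Section 3 gives enrollment goals of 185 (prior entecavir), 33 (prior TDF) and 33 (prior combination). 185 + 33 + 33 = 251, which matches the stated total. Section 8 bases the sample size on feasibility. It states no drop-out rate and no expected suppression rate, so the effect cannot be computed from the documents.

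**3. Illustration, with assumed inputs**

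Let w be the share withdrawn, p_R the suppression rate in those retained, and p_W the rate in those withdrawn.

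- Rate reported under Section 8: p_R
- Rate in all enrolled: (1 − w) × p_R + w × p_W
- Difference: w × (p_R − p_W)

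Assume p_R = 95% and p_W between 70% and 95%. At p_W = 95% the difference is zero for every w. At p_W = 70% it is w × 25 points:

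| w (assumed) | Withdrawn, of 251 | Left in analysis | All-enrolled rate at p_W = 70% | Range of upward shift, points |
|---|---|---|---|---|
| 5% | 13 | 238 | 93.75% | 0 to 1.3 |
| 10% | 25 | 226 | 92.5% | 0 to 2.5 |
| 20% | 50 | 201 | 90.0% | 0 to 5.0 |

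For example, at w = 10% the all-enrolled rate is 0.90 × 95% + 0.10 × 70% = 92.5%, and 95% − 92.5% = 2.5 points.

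The table counts everyone withdrawn, for whatever reason. Changing the rules can restore only those who have a result at the time point in question.

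**The case against.** Much can be said for the plan. The bullet says patients may be considered withdrawn, so a site can leave a late attender in the study, and the flexible visit interval means that a late visit is not obviously a failure to return. The investigator must report the reasons for and nature of each withdrawal, with the last encounter and laboratory tests, so refusal and absence could be told apart afterwards. The paragraph on follow-up visits is headed as concerning withdrawal from the investigational product, so its authors may have had patients who stop the drug in mind. On this view the defect is one of wording.

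Two stronger readings are tempting, and the objection defeats both:

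- A reader might infer that data collection stops for patients who never refused. It does not, in general. The data rule leaves out only those lost to follow-up, and a patient still seen in the clinic is, on an ordinary reading, not lost. No text closes the clinic record because of the reason label. It follows that no count of HBV DNA results lost to collection can be derived from this rule.
- A reader might infer that the plan collects data from refusers without their consent. The consent pages are not among the documents under review and may provide for continued record abstraction. What can be said is that the protocol text shows no exception.

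The rest of the objection does not dispose of the point. The permissive bullet is followed by a mandatory sentence, so sites may differ. A recorded reason does not put a withdrawn patient back into the Section 8 analysis set. The follow-up paragraph's text speaks of withdrawal from the study, whatever its heading says.

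**Conclusion.** The concern holds as a conflict between collection and analysis. Section 6 allows, and in one sentence requires, that patients who miss study visits be withdrawn under a consent heading, and it keeps collecting their routine results. Section 8 then leaves them out. The reported suppression rate therefore describes those never withdrawn, and it is too high if non-attenders are less often suppressed.

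The direction rests on that last assumption, which the documents neither support nor contradict. The size is unknown: 0 to 2.5 points at 10% withdrawn is an illustration on assumed rates, not an estimate for this trial. If suppression is the same in both groups, the shift is zero, and the cost is only lost precision.

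The absence of a visible exception for revoked consent in the post-withdrawal visit and data rules is a separate gap in the text and needs no assumption. The change should be made: it alters who is analysed for the primary endpoint, and it costs little.

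**What to change.** Replace the single criterion in Section 6 with three, and state for each whether the patient is withdrawn:

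- **Consent withdrawn by the patient's statement.** Later study visits are offered, not required. Later data are collected only as far as the patient's consent allows.
- **Study visit missed, patient still in care.** The patient is not withdrawn and stays in the study and in the analysis set. Routine HBV DNA, ALT, creatinine and DEXA results are abstracted from the clinic record.
- **Lost to follow-up.** Declared only after documented contact attempts and a check of the clinic record for results.

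Reconcile the permissive bullet with the mandatory sentence that follows it. Limit the early discontinuation and 3 to 6 month visit rules to patients who can attend and have not refused.

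Align Section 8 so that data collected before withdrawal, and data permitted after it, stay in the analysis. Report the number in each of the three groups at each time point.

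The cost is protocol wording, CRF reason codes and modest extra record abstraction at sites for the second group. No new tests or visits are added.
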